#### **7.1.6. Summaries of Adverse Events and Deaths**

Treatment-emergent AEs will be summarized based on the Safety Analysis Set for the Randomized Treatment Phase (up to the last dose at Week 24) and the Overall Treatment Phase (up to the last dose of any study drug plus 28 days).

A brief, high-level summary of the number and percentage of subjects who experienced at least 1 TEAE in the categories described below will be provided by treatment group. The brief summary will also include treatment-related TEAEs, and treatment-related TE SAEs. In addition, a table for each category showing the number and percentage of subjects will be provided by PT and treatment group in descending order of total frequency:

- TEAEs
- TEAEs by severity grade
- TEAEs related to VBR
- TEAEs related to ETV
- TEAEs related to Peg-IFN $\alpha$
- TE SAEs
- TE SAEs related to VBR
- TE SAEs related to ETV
- TE SAEs related to Peg-IFN $\alpha$
- TEAEs leading to VBR discontinuation
- TEAEs leading to ETV discontinuation
- TEAEs leading to Peg-IFN $\alpha$  discontinuation

- TEAEs leading to study discontinuation
- COVID-19 specific TEAEs
- COVID-19 specific TE SAEs

Multiple events will be counted only once per subject in each summary. For summary by severity grade, the most severe grade will be used for those AEs that occurred more than once in an individual subject during the study.

For the Follow-up Phase, a summary table will also be provided for all the AEs that occurred after the last dose of any study drug + 28 days through the end of study by the above category and by PT.

A data listing containing all AEs will be provided.

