 Final study drug dispensation of Peg-IFN $\alpha$  will occur at Week 20, 731 at Week 44, and ETV at Week 56. Final study drug accountability of Peg-IFN $\alpha$  is performed at Week 24, 731 at Week 48, and ETV at Week 60.

 731 and ETV administration are in-clinic at the study visits and self-administered once daily at home on all other days. Day 1 Peg-IFN $\alpha$  administration is in-clinic for injection training purposes; subsequently, subjects will administer Peg-IFN $\alpha$  once weekly at home.

 Dosing with Peg-IFN $\alpha$  (if applicable) will stop at Week 24. Dosing with 731 (if applicable) will stop at Week 48. Dosing with ETV will continue until Week 60.

 If the subject inadvertently administers study drug prior to collection, a PK sample should still be drawn. Refer to [Section 7.11](#).

 Predose PK samples for 731, ETV, and Peg-IFN $\alpha$  on Day 1 and Weeks 4 and 24. Postdose PK samples for 731, ETV, and Peg-IFN $\alpha$  may be collected from 2 to 4 hours postdose on Day 1, and between 30 min and 2 hours after in-clinic study drug administration at Weeks 2, 8, 12, and 24. Postdose samples at Weeks 16 and 20 may be collected between 4 and 6 hours after in-clinic study drug administration. Predose samples for ETV may be collected at Week 44.

 HBcAb IgM testing may be performed for some subjects at Screening, see Inclusion Criterion #5, [Section 5.2](#).

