## 1.2. Study Design

[figure not shown]
This study will assess the safety, antiviral activity, and PK of VBR administered in combination with ETV with or without Peg-IFN $\alpha$  in treatment-naïve, HBeAg positive Chinese subjects with cHBV. The study will be conducted at approximately 5 to 10 study sites in China.

Approximately 60 eligible subjects with HBeAg positive cHBV will be randomly assigned in a 1:1:1 ratio to the treatment groups shown in the study overview presented in [Figure 1-1 Study Overview](#).

Treatment with VBR and/or ETV will be administered orally, once daily; treatment with Peg-IFN $\alpha$  will be administered subcutaneously, once weekly. Group 1 will receive VBR+ETV for 24 weeks, Group 2 will receive VBR+ETV+Peg-IFN $\alpha$  for 24 weeks and Group 3 will receive ETV+Peg-IFN $\alpha$  for 24 weeks. All subjects will receive VBR+ETV from Week 24 through Week 48 and then ETV alone from Week 48 through Week 60 during the 12-week follow-up period.

Treatment assignments will be stratified by the HBV genotype (GT; ie, GT A or B vs GT C or D, vs other GTs) and baseline ALT (ie, ALT  $<5 \times$  upper limit of normal [ULN] vs ALT  $\geq 5 \times$  ULN) during the Screening visits.

**Figure 1-1** Study Overview

Abbreviations: BL = Baseline; ETV = entecavir; Peg-IFN $\alpha$  = pegylated-interferon alpha; Wk = week.

Note: ABI-H0731 is the former designation for VBR.

The schedule of study procedures is presented in tabular form in Appendix 1 of the study protocol.

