#### **3.2. Subject Grouping**

For analyses based on the All Randomized Analysis Set and FAS, subjects will be grouped according to the treatment to which they were randomized. For analyses based on the Safety Analysis Set, subjects will be grouped according to the actual treatment received. The actual treatment received will differ from the randomized treatment only when their actual treatment differs from randomized treatment for the entire treatment duration.

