### **3.6. Analysis Visit Windows**

#### **3.6.1. Definition of Study Drug**

In this study, study drugs are defined as VBR, ETV, and Peg-IFN $\alpha$ .

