#### **3.6.2. Definition of Study Phase**

The following phases will be defined: Randomized Treatment Phase and Overall Treatment Phase are on treatment; and the Follow-up Phase is off treatment.

- Randomized Treatment Phase: from first dose date through Week 24 visit (or premature termination visit if before Week 24)
- Overall Treatment Phase: from first dose date through Week 48 visit (or premature termination visit if before Week 48)
- Follow-up Phase: after Week 48 visit (or premature termination visit) through end of study

End of study will be when the subject completes the last visit of the follow-up period or is considered “lost to follow-up,” whichever is later.

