#### **3.6.3. Definition of Study Day**

The first dose date of VBR when administered in combination with ETV with or without Peg-IFN $\alpha$  will be calculated where applicable. Study Day 1 is defined as the first dose date of study drug, which is the earliest/minimum of the first dose dates of VBR, ETV, and Peg-IFN $\alpha$  in a treatment group. If the first dose date is missing, the date of randomization will be used.

The last dose date of VBR, ETV, and of Peg-IFN $\alpha$  will be calculated where applicable. For the Randomized Treatment Phase, the last dose date of study drug VBR will be the Week 24 visit date or the end date on study drug administration CRF if a subject discontinued study drug prior to Week 24 visit. For study drug ETV, the last dose date will be obtained from End of Treatment-ETV eCRF. For study drug Peg-IFN $\alpha$ , the last dose date will be obtained from End of Treatment-Peg-IFN $\alpha$  eCRF. For the Overall Treatment Phase, the last dose date for each drug will be the end date on the respective End of Treatment eCRF pages. The last dose date of study drug will be defined as the latest/maximum of the last dose dates of VBR, ETV, and Peg-IFN $\alpha$  in a treatment group.

For the on-treatment phases, Study Day will be calculated from Study Day 1 and derived as follows:

- For days prior to the first dose: Assessment Date – Study Day 1
- For postdose study days: Assessment Date – Study Day 1 + 1

For the Follow-up Phase, the follow-up Study Day 1 is defined as the day after Week 48 visit or Premature Termination visit. The follow-up study day will be derived as Assessment Date – follow-up Study Day 1 +1.

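### The Overall Treatment Phase safety tables run past the phase's Week 48 end into ETV-only follow-up, and no incidence table isolates Group 3's first 24 weeks on VBR

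*Combined protocol and SAP*

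**What the plan says.** The treatment sequence is in SAP 1.2: "All subjects will receive VBR+ETV from Week 24 through Week 48 and then ETV alone from Week 48 through Week 60". Group 3 is on ETV+Peg-IFN before that, so Week 24 is its first exposure to VBR (called 731 in the protocol).

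SAP 3.6.2 defines the phases. It reads "Overall Treatment Phase: from first dose date through Week 48 visit (or premature termination visit if before Week 48", and it adds that "the Follow-up Phase is off treatment". SAP 4.2.1 and 4.2.2.1 agree, with an expected Overall duration of 48 weeks and 336 ETV tablets.

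The safety tables use a different end. SAP 7.1.6 defines "the Overall Treatment Phase (up to the last dose of any study drug plus 28 days", and SAP 7.2.1.1 and 7.2.1.2 apply the same 28-day extension to graded laboratory abnormalities. The follow-up AE table in 7.1.6 opens only once that window has closed. The follow-up laboratory summary in 7.2.1.2 belongs to the Follow-up Phase, which SAP 3.6.3 and 3.6.4 start on the day after the Week 48 or premature termination visit.

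ETV sets the end date. SAP 3.6.1: "In this study, study drugs are defined as VBR, ETV, and Peg-IFN". SAP 3.6.3: "The last dose date of study drug will be defined as the latest/maximum of the last dose dates of VBR, ETV", with Peg-IFN completing the list. Protocol Appendix 1, footnote 19, on Peg-IFN, then 731, then ETV: "will stop at Week 24. Dosing with 731 (if applicable) will stop at Week 48. Dosing with ETV will continue until Week 60".

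On labels, SAP 3.2 says: "The actual treatment received will differ from the randomized treatment only when their actual treatment differs from randomized treatment for the entire treatment duration". Group 3 therefore stays in the ETV+Peg-IFN column while it is taking VBR.

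**The concern.** The safety and tolerability of VBR is the primary objective, and two features of the tables work against it.

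First, one phase name has two end dates. Under the later one, events that arise after VBR has stopped are tabulated as on treatment. The follow-up AE table then has little or nothing left to show, and a reader of the report could take that as an absence of events after VBR. Laboratory abnormalities from the same weeks would appear in both the Overall and the follow-up summaries.

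Second, Group 3 is the only group that starts VBR after 24 weeks without it. Its all-cause AEs and graded laboratory abnormalities on VBR are pooled with 24 weeks on Peg-IFN, whose common side effects include cytopenias (Protocol 2.1). No incidence table starts at Week 24, and the baseline for grading stays before the first dose of any drug (SAP 3.6.4).

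**Working it through.** **Inputs.** Weeks 24 and 48 are Days 168 and 336 (SAP Table 3-1). Week 60 is 60 × 7 = Day 420. The Week 60 visit window is ±5 days (Protocol 7.7), so the latest visit is Day 425. About 60 subjects are randomized 1:1:1, or about 20 per group (SAP 1.3).

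**1. The plan's own figures.** 24 + 24 = 48 weeks; ETV 7 × 48 = 336 tablets; VBR 3 × 7 × 48 = 1008 tablets. All match SAP 4.2.1 and 4.2.2.1, so those sections follow the phase definition in 3.6.2.

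**2. The window in the safety tables, for a completer.**

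| | Overall window ends | Of the 84 follow-up days (420 − 336), in Overall | Left for the follow-up AE table |
|---|---|---|---|
| SAP 3.6.2 | Day 336 | 0 | 84 |
| SAP 7.1.6 and 7.2.1.1, ETV end = Week 60 | 420 + 28 = Day 448 | 84 | 0 |
| Same, if the ETV page holds Week 48 | 336 + 28 = Day 364 | 28 | 56 |

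Day 448 is 23 days after Day 425, so on the literal reading the follow-up AE window opens after a completer's last visit.

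**3. Laboratory overlap.** Follow-up laboratory data start the day after the Week 48 visit, while the Overall table takes results to Day 448 (or Day 364). The overlap is again 84 (or 28) days.

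**4. Early termination.** SAP 1 says that participants ended study treatment and then had 12 weeks of ETV. For a subject who stops at week T, section 3.6.2 ends the phase at T. The table window ends at T + 12 + 4 = T + 16, and the study at about T + 12. If the ETV page holds T, the window ends at T + 4. The conflict is the same as for completers.

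**5. What the Group 3 Overall column contains.** With the window set by ETV at Week 60, treatment time is 168 days on ETV+Peg-IFN, 168 on VBR+ETV and 84 on ETV alone. VBR time is 168/420 = 40%, against 336/420 = 80% in Groups 1 and 2. Under section 3.6.2 the shares would be 168/336 = 50% and 100%.

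**6. Can Weeks 24–48 be recovered by subtracting the Week 24 table?** SAP 7.1.6 counts a subject once per summary, and 7.2.1.2 keeps only the worst grade. The rates below are assumptions, with the two periods independent and n = 20.
- Any-TEAE row: with incidence p1 by Week 24 and p2 in Weeks 24–48, subtraction shows 20 × (1 − p1) × p2 subjects out of 20 × p2. At p2 = 20% (4 subjects), it shows 2.0 if p1 = 50% and 0.2 if p1 = 95%.
- A single preferred term with p1 = 10% and p2 = 20%: 20 × 0.10 × 0.20 = 0.4 of 4 subjects are hidden, and more if events cluster within subjects.

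Subtraction therefore works fairly well for terms that are new after Week 24. It fails for the any-TEAE row, for terms repeated in the same subject, and for worst-grade laboratory counts.

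**The case against.** The strongest reply is that a treatment-emergent window that outlasts dosing by 28 days is ordinary practice (SAP 7.1.5.1 defines TEAEs that way), and that visit phases and TEAE windows need not coincide. That is right, and the tail itself is no fault. The defect is narrower: the tail hangs on any study drug, follow-up ETV is one, and the tables reuse the name of a phase that ends at Week 48.

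A second reply is that SAP 3.6.3 takes the last dose date from the End of Treatment pages, and that several passages speak of treatment as over before follow-up ETV begins. If the ETV page holds Week 48, 28 days are absorbed and the follow-up AE table keeps 56. This stands as a limit on size. It does not remove the conflict.

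A third is that much of the Week 24–48 information is already planned: AE and laboratory listings, by-visit summaries, and rows for VBR-related events and VBR discontinuation, which in Group 3 can in practice arise only after Week 24. This also stands, but the VBR-related rows rest on open-label attribution, and none of these sources gives all-cause incidence.

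A reader might infer more than the documents support:
- That no table covers Weeks 24–48. The Overall tables do cover it; they do not isolate it.
- That subtraction recovers nothing. New preferred terms do appear.
- That the randomized comparison of Groups 2 and 3 to Week 24 is damaged. It has its own phase and is unaffected.
- That the termination date of 25 July 2022 (SAP 2.2) fixes who reached Week 24. The documents give neither first-dose dates nor the date on which dosing stopped.

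**Conclusion.** The concern holds, and the SAP should be changed. SAP 7.1.6, 7.2.1.1 and 7.2.1.2 conflict with 3.6.2 by 28 to 84 days per completer, depending on which date the End of Treatment-ETV page records. On the literal reading (ETV as study drug to Week 60), all 84 ETV-only days count as on treatment and a completer's follow-up AE window is empty. A subject who stops ETV early could still have follow-up AE time. Follow-up laboratory abnormalities fall in two tables on either reading, for 84 or 28 days.

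Separately, no AE or graded-laboratory incidence table isolates Group 3's first exposure to VBR. This is a gap in reporting and not a bias in a planned comparison. The number of Group 3 subjects who passed Week 24 is not given and could be anywhere from 0 to about 20, so the documents do not show that any reported result was distorted.

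**What to change.** 1. Reconcile SAP 7.1.6, 7.2.1.1 and 7.2.1.2 with 3.6.2. The on-treatment analysis window should not absorb ETV-only follow-up (for example, follow-up ETV would not set its end), the follow-up tables should contain that period, and each event should fall in one phase.

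2. Add a descriptive Week 24–48 VBR+ETV table of TEAEs and treatment-emergent laboratory abnormalities by randomized group:
   - use the number entering the period as denominator, and identify Group 3 as newly starting VBR;
   - grade laboratory changes against both the Day 1 and the Week 24 values, because a Week 24 baseline alone would hide abnormalities already present on Peg-IFN;
   - note that Groups 2 and 3 both stop Peg-IFN at that visit, with Group 2, which continues VBR, as the concurrent reference.

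The cost is SAP wording and one extra table set, with no new data. SAP 1 already provides for recording changes made after finalization in the synoptic report. The downsides are confounding by Peg-IFN withdrawal, which Group 2 addresses only in part, and possibly small denominators. With zero events, the exact two-sided 95% upper limit 1 − 0.025^(1/n) is 16.8%, 30.8% or 52.2% for n = 20, 10 or 5, so an empty row would not be strong reassurance.

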Currently, there are 2 clinically accepted, first-line treatment options for CHB: nucleos(t)ide reverse transcriptase inhibitors of the HBV polymerase (NrtIs) and interferon alfa (IFN $\alpha$ ). The NrtIs are orally administered, potent, direct-acting antivirals targeting the reverse transcription of HBV pgRNA to DNA. They are broadly used, generally safe and well-tolerated and have demonstrated success in achieving and maintaining viral suppression in most patients ([Lampertico & Liaw 2012](#)). However, despite suppression of HBV DNA for extended periods of time with NrtI treatment, HBeAg and HBsAg loss is uncommon and the template for ongoing viral replication, cccDNA, is not eliminated in most patients. As a result, off-treatment SVR with NrtIs is rare, necessitating long-term chronic suppressive treatment. In contrast, IFN $\alpha$  is an approved, subcutaneously administered protein which directly and indirectly targets HBV. While the specific mechanism of action is not fully understood, it is thought that IFN $\alpha$  inhibits multiple steps in the viral lifecycle resulting in modest antiviral activity ([Konerman & Lok 2016](#)). In addition, IFN $\alpha$  augments innate immunity and triggers HBV-specific T cell responses. Pegylated (Peg)-IFN $\alpha$  is the preferred formulation due to increased pharmacokinetic (PK) and pharmacodynamic half-life supporting weekly dosing. The recommended treatment duration is 48 weeks. Compared with NrtIs, IFN $\alpha$  is poorly tolerated due to common side effects, including flu-like symptoms, mood disturbances, and cytopenias. With a finite treatment duration, IFN $\alpha$  results in a higher rate of durable virologic response and modest HBeAg and HBsAg loss. However, even with the incremental improvements in virologic response of Peg-IFN $\alpha$  monotherapy, this regimen remains suboptimal and is offset by its safety and tolerability profile.

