#### **10.3.6.1. Treatment-emergent Adverse Events**

Treatment-emergent adverse events reported during the study will be coded using the Medical Dictionary for Regulatory Activities (MedDRA) dictionary. Incidence of TEAEs will be summarized by treatment group and the following:

- Preferred term
- System organ class and preferred term
- System organ class, preferred term, and severity

These summaries will be presented for the following TEAE categories:

- All AEs
- SAEs
- Drug-related AEs

For tables reporting adverse events by severity, if a subject has multiple occurrences of an AE with the same system organ class and preferred term, the most severe event will be presented.

All AEs will be recorded from the first dose of study drug (731, ETV, or Peg-IFN $\alpha$ ) until the last study visit.

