## 7. SAFETY ANALYSES

### 7.1. Adverse Events and Deaths

#### 7.1.1. Adverse Event Dictionary

Clinical and laboratory adverse events (AEs) will be coded using the Medical Dictionary for Regulatory Activities (MedDRA) Version (v) 23.1. System organ class (SOC), high-level group term (HLGT), high-level term (HLT), preferred term (PT), and lower-level term (LLT) will be provided in the AE dataset.

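### SAP 7.1.6 tabulates adverse events by preferred term only and omits, without naming it as a change, the system-organ-class tables planned in protocol 10.3.6.1

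*Combined protocol and SAP*

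**What the plan says.** Protocol 10.3.6.1 plans TEAE incidence by treatment group at three levels: PT alone, "System organ class and preferred term", and "System organ class, preferred term, and severity". It applies all three to all AEs, to SAEs and to drug-related AEs.

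SAP 7.1.6 first plans a high-level count per arm of subjects with at least one TEAE in each of 15 categories (for example any TEAE, by grade, related to each drug, serious, leading to discontinuation of each drug). It then states that "a table for each category showing the number and percentage of subjects will be provided by PT and treatment group". The Follow-up Phase table likewise runs "through the end of study by the above category and by PT". A listing is added: "A data listing containing all AEs will be provided".

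SAP 7.1.1 says that the SOC and the intermediate dictionary levels "will be provided in the AE dataset", but no table in the SAP uses them.

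Four SAP sections speak of reduced scope after early termination. Section 1 limits the work to key safety and efficacy endpoints, 2.2 refers to a synoptic report, 6.2 lists changes to efficacy analyses, and 7.6 drops additional safety measures. None mentions the SOC tables.

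**The concern.** Adverse events are part of the primary endpoint (protocol 3.2.1), so the AE tables carry the main result of the study. A PT is a narrow label. Events that a clinician would regard as one kind of harm can be coded to several PTs, and with about 20 subjects per arm each row may hold only a few cases. The SOC row counts each affected subject once across those labels and makes the arms comparable for that class.

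Protocol 2.1 describes Peg-IFNα as having "common side effects, including flu-like symptoms, mood disturbances, and cytopenias". Mood disturbance is the clearest example. Protocol Appendix 3 has a Psychiatric heading with separate rows for insomnia, for psychiatric disorders (anxiety, depression, mania, psychosis) and for suicidal ideation or attempt. Events of these kinds would ordinarily be coded to different PTs, so PT tables alone give no psychiatric total for either of the two Peg-IFNα arms or for the arm without it.

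**Working it through.** **Step 1: the two documents side by side.**

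| Level of TEAE table, by arm | Protocol 10.3.6.1 | SAP 7.1.6 |
|---|---|---|
| PT | planned | planned |
| PT by severity grade | not listed separately | planned |
| SOC and PT | planned | absent |
| SOC, PT and severity | planned | absent |

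The plan states no figure on this point, and neither document gives an expected AE rate or a sample-size calculation. There is nothing to reproduce.

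**Step 2: can the missing class totals be read from the PT tables?** SAP 7.1.6 counts a subject once per summary however many events he or she had. In a PT table this works row by row, so a subject with two different PTs of one class stands in two rows. Let the PTs of a class have counts c1, ..., cm in an arm of n subjects. The number C of distinct subjects with any event in the class then satisfies

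max(ci) ≤ C ≤ min(n, c1 + ... + cm).

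The lower bound is reached when the same subjects have all the events, the upper bound when no subject has two. The bound assumes nothing about correlation between terms.

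**Step 3: numbers.** Arm size: about 60 subjects randomized 1:1:1 (protocol 10.1), so n = 60/3 = 20. The PT counts are assumed: three PTs in one class, with the same count in each.

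| Subjects per PT row | Lower bound for C | Upper bound for C | Class incidence |
|---|---|---|---|
| 1 | 1 | 3 × 1 = 3 | 1/20 to 3/20 = 5% to 15% |
| 2 | 2 | 3 × 2 = 6 | 2/20 to 6/20 = 10% to 30% |
| 3 | 3 | 3 × 3 = 9 | 3/20 to 9/20 = 15% to 45% |

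In each line the same three PT rows fit a threefold range of class incidence. Exact (Clopper-Pearson) 95% intervals at the two ends of the middle line are 1.2% to 31.7% for 2/20 and 11.9% to 54.3% for 6/20. Sampling uncertainty is wide at this size in any case. The PT-only layout adds a second uncertainty that the collected data could remove entirely.

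**Step 4: is the omission declared?** The statements in SAP 1, 2.2 and 7.6 are general, and 6.2 concerns efficacy. AE tables are not an additional measure within the meaning of 7.6, because 7.1.6 keeps them and only changes their structure. The restriction to key safety endpoints does not account for the change either, since AEs belong to the primary endpoint.

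**The case against.** The other side has a good deal in its favour. The study was stopped early, the output is a synoptic report, and the SAP says openly that safety work is cut back. The components of the primary endpoint are still reported per arm: the high-level TEAE summary, the disposition table (SAP 4.1) and the laboratory tables (SAP 7.2.1.2). The high-level summary also gives, per arm and across PTs, the subjects with TEAEs related to Peg-IFNα and with TEAEs leading to its discontinuation. No formal inference is planned.

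A reader might infer something stronger: that the incidence of the Peg-IFNα harms named in protocol 2.1 will go unreported. The documents do not support that.

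- Cytopenias are reported per arm by laboratory test at worst grade, and Appendix 3 grades neutrophils, white cells, platelets, hemoglobin and lymphocytes. Only a combined cytopenia count is lacking.
- Flu-like symptoms are a cluster. Appendix 3 puts fever, chills and fatigue under Systemic, myalgia under Musculoskeletal and headache under Neurologic. These headings are not the dictionary's SOCs, but they suggest that SOC rows would not give one figure either.
- The three harms appear in the protocol as background, not as endpoints or events of special interest.
- The dataset and the listing allow any class count to be derived later.

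All of this narrows the point without removing it. A general scope statement does not tell the reader that two protocol tables have gone. Brevity is not an evident reason either, because the same SAP keeps a class level for medications (ATC Level 2, sections 7.4.1 and 7.4.2) and 15 AE categories.

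**Conclusion.** The point holds as an undeclared difference between protocol and SAP in the reporting of the primary safety objective. Totals of distinct subjects per organ class and arm are not planned, and adding PT rows cannot supply them. Psychiatric events show this best.

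The size can be given only by example. Three PTs at 2 of 20 leave a class incidence anywhere from 10% to 30%. This rests on assumed PT counts, on about 20 subjects per arm as planned, and on the events being coded to different PTs within one SOC. The documents give no rates from which to say how wide the range will be in practice.

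The conclusion does not extend to cytopenias, which have their own tables, or to flu-like symptoms, for which SOC tables alone would probably not be enough. The counts are untabulated, not unrecoverable.

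**What to change.** In SAP 7.1.6, restore the tables by SOC and PT, and by SOC, PT and maximum grade, by arm, for all TEAEs, serious TEAEs and drug-related TEAEs, in both the Randomized Treatment Phase and the Overall Treatment Phase. State that each subject is counted once per SOC and once per PT. The protocol's own rule covers only repeat events within the same SOC and PT, so this needs to be written down. If the sponsor prefers to omit the tables, the SAP should name the omission and give the reason.

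Optionally, if mood or flu-like events are to be reported as groups, fix the list of PTs before database lock so that the grouping is not chosen after the data are seen. This goes beyond what the protocol promises.

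The cost is SAP wording and slightly longer tables. The SOC codes are already in the AE dataset, so no new data are needed. If the SAP is already final, its section 1 allows the change to be documented in the synoptic report.
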